**Figure 8 Distribution of influenza types by region - <country> (Total cohort)**

**Template 15 Summary of influenza A subtypes by region - <country> (Total cohort)**

		West N=XX			Central N=XX			Panama N=XX			Northeast N=XX			Total N=XX			
Influenza A subtypes	Categories	n	%	95% CI		n	%	95% CI		n	%	95% CI		n	%	95% CI	
				LL	UL			LL	UL			LL	UL			LL	UL
H1N1	Positive																
	Negative																
	Missing/Unknown	-	-	-	-	-	-	-	-	-	-	-	-	-	-	-	-
H3N2	Positive																
	Negative																
	Missing/Unknown	-	-	-	-	-	-	-	-	-	-	-	-	-	-	-	-

N = number of influenza positive specimens by age group

n = number of specimens in a given category

% = n / Number of specimens with available results x 100

[figure not shown]
95%CI= exact confidence interval; LL=lower limit; UL=upper limit

West: Boca del Toro, Chiriquí and Comarca Nobe Bugle

Central: Coclé, Herrera, Los Santos and Veraguas

Panamá: Panamá Este, Panamá Oeste, Panamá Metro and San Miguelito

Northeast: Colón, Darién and Kuna Yala

**Figure 9 Distribution of influenza A subtypes by region - <country> (Total cohort)**

**Template 16 Summary of influenza B lineage by region - <country> (Total cohort)**

		West N=XX		Central N=XX		Panama N=XX			Northeast N=XX			Total N=XX			
Influenza B lineage	Categories	n	%	N	%	95% CI		n	%	95% CI		n	%	95% CI	
						LL	UL			LL	UL			LL	UL
Victoria	Positive														
	Negative														
	Missing/Unknown	-	-	-	-	-	-	-	-	-	-	-	-	-	-
Yamagata	Positive														
	Negative														
	Missing/Unknown	-	-	-	-	-	-	-	-	-	-	-	-	-	-

N = number of influenza positive specimens by age group

n = number of specimens in a given category

% = n / Number of specimens with available results x 100

[figure not shown]
95%CI= exact confidence interval; LL=lower limit; UL=upper limit

West: Boca del Toro, Chiriquí and Comarca Nobe Bugle

Central: Coclé, Herrera, Los Santos and Veraguas

Panamá: Panamá Este, Panamá Oeste, Panamá Metro and San Miguelito

Northeast: Colón, Darién and Kuna Yala

**Figure 10 Distribution of influenza B lineage by region - <country> (Total cohort)**

**Template 17 Proportion of Influenza caused by influenza A and/or B among all influenza cases by calendar year - <country> (Total cohort)**

Calendar year	Influenza type				95% CI	
		n	N	%	LL	UL
2010	Influenza A					
	Influenza B					
2011	Influenza A					
	Influenza B					
2012	Influenza A					
	Influenza B					
2013	Influenza A					
	Influenza B					
2014	Influenza A					
	Influenza B					
2015	Influenza A					
	Influenza B					
2016	Influenza A					
	Influenza B					
Total	Influenza A					
	Influenza B					

N = Number of Influenza positive specimens with available test results by year

n = Number of positive specimens in a given category

% =  $(n/N) * 100$

95%CI= exact confidence interval; LL=lower limit; UL=upper limit

**Template 18 Proportion of Influenza caused by influenza A and/or B among all influenza cases by influenza season - <country> (Total cohort)**

<Southern/northern hemisphere Influenza season>	Influenza type				95% CI	
		n	N	%	LL	UL
May– Oct 2010	Influenza A					
	Influenza B					
May– Oct 2011	Influenza A					
	Influenza B					
May– Oct 2012	Influenza A					
	Influenza B					
May– Oct 2013	Influenza A					
	Influenza B					
May– Oct 2014	Influenza A					
	Influenza B					
May– Oct 2015	Influenza A					
	Influenza B					
May– Oct 2016	Influenza A					
	Influenza B					
Total	Influenza A					
	Influenza B					

[figure not shown]
N = Number of Influenza positive specimens with available test results by year

n = Number of positive specimens in a given category

% =  $(n/N) * 100$

95%CI= exact confidence interval; LL=lower limit; UL=upper limit

**Figure 11 Distribution of Influenza caused by influenza A and/or B among all influenza cases by calendar year - <country> (Total cohort)**

**Figure 12 Distribution of Influenza caused by influenza A and/or B among all influenza cases by influenza season - <country> (Total cohort)**

Refer to [Figure 11](#)

**Template 19 Proportion of Influenza A subtypes among all influenza cases by calendar year - <country> (Total cohort)**

Year	Influenza A subtypes	n	N	%	95% CI
					LL
					UL
2010	H1N1				
	H3N2				
2011	H1N1				
	H3N2				
2012	H1N1				
	H3N2				
2013	H1N1				
	H3N2				
2014	H1N1				
	H3N2				
2015	H1N1				
	H3N2				
2016	H1N1				
	H3N2				
Total	H1N1				
	H3N2				

N = Number of Influenza positive specimens with available test results by year

n = Number of positive specimens in a given category

% = n/N \* 100

95%CI= exact confidence interval; LL=lower limit; UL=upper limit

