6.5.3. Extraction of individual data

All seasonal influenza A and/or B cases reported in the ICGES database will be validated and extracted in the required file format e.g. Statistical Analysis System (SAS) datasets. The following data will be collected for seasonal influenza A and/or B positive subjects:

- Demographic data such as age and gender.
- Data on A-virus subtype and B-strain lineage (when available), geographic region, clinical features and outcomes (clinical manifestations, duration of illness, complications) etc.

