#### 11.2.2. Demography

- Age at date of onset of the first symptom, will be expressed in years in the study. This will be computed as the difference between the date of onset of the first symptom and the date of birth (only if the data is available).
- The percentages will be computed by using only available information. Only frequencies will be provided for unknown or missing or not applicable categories
- Any measurements omitted or non-evaluable for a particular subject or analysis will not be replaced. Therefore, subjects with omitted or non-evaluable measurements will be excluded from the analysis

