**Template 7 Distribution of influenza A subtype H1N1 cases by month and year - <country> (Total cohort)**

Month and year (date of onset of symptoms)	Influenza virus positive (N)	Influenza A subtype H1N1 (n)	Percentage (%)
Jan2010			
Feb2010			
Mar 2010			
Apr2010			
May2010			
Jun2010			
Jul2010			
Aug2010			
Sep2010			
Oct2010			
Nov2010			
Dec2010			
Jan2011			
Feb2011			
....			
Dec2016			

N = number of influenza positive specimens with available test results by month and year

n = number of influenza A subtype H1N1 specimens in a given category

% = (n / N) x 100

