**Figure 5 Distribution of influenza types by age group - <country> (Total cohort)**

**Template 12 Summary of influenza A subtypes by age group - <country> (Total cohort)**

[figure not shown]
		0-4 N=XX			5-17 N=XX			... N=XX			Total N=XX		
Influenza A sub-type	Categories	n	%	95% CI		n	%	95% CI		n	%	95% CI	
				LL	UL			LL	UL			LL	UL
H1N1	Positive												
	Negative												
	Missing/Unknown	-	-	-	-	-	-	-	-	-	-	-	-
H3N2	Positive												
	Negative												
	Missing/Unknown	-	-	-	-	-	-	-	-	-	-	-	-

N = number of influenza positive specimens by age group

n = number of specimens in a given category

% = n / Number of specimens with available results x 100

95%CI= exact confidence interval; LL=lower limit; UL=upper limit

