**Template 21 Proportion of Influenza B lineage among all influenza cases by calendar year - <country> (Total cohort)**

Year	Influenza B lineage	n	N	%	95% CI	
					LL	UL
2010	Victoria					
	Yamagata					
2011	Victoria					
	Yamagata					
2012	Victoria					
	Yamagata					
2013	Victoria					
	Yamagata					
2014	Victoria					
	Yamagata					
2015	Victoria					
	Yamagata					
2016	Victoria					
	Yamagata					
Total	Victoria					
	Yamagata					

N = Number of Influenza positive specimens with available test results by year

n = Number of positive specimens in a given category

% =  $n/N * 100$

95%CI= exact confidence interval; LL=lower limit; UL=upper limit

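### SAP Templates 7-10 and 19-22 do not define the denominator for subtype and lineage shares; on the natural reading the shares fall with the fraction of specimens typed

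*SAP*

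**What the plan says.** The calendar-year tables are titled "Proportion of Influenza A subtypes among all influenza cases by calendar year" (Template 19) and "Proportion of Influenza B lineage among all influenza cases by calendar year" (Template 21); Templates 20 and 22 repeat them by season. All four define the denominator as "N = Number of Influenza positive specimens with available test results by year". Templates 17-18, which split influenza into A and B, use the same words.

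The monthly tables (Templates 7 and 9, to which 8 and 10 refer) label the N column as influenza virus positives, with the footnote "N = number of influenza positive specimens with available test results by month and year".

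None of these eight templates has a row for specimens without a subtype or lineage. Protocol section 6.5.3 shows that such specimens are expected: "Data on A-virus subtype and B-strain lineage (when available), geographic region". Protocol section 1.2 adds that strain typing of B isolates is not routine in the other participating countries.

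Elsewhere the SAP treats unknown results differently. Section 11.2.2 says "The percentages will be computed by using only available information", with unknown or missing categories shown as counts only. Templates 12, 13, 15 and 16 have a Missing/Unknown row and compute the percentage as "n / Number of specimens with available results x 100". Template 23, the lineage match table, uses the same denominator rule.

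**The concern.** A specimen that is positive for influenza A but not subtyped has an influenza test result. If N is all influenza positives, that specimen is counted in N but can appear in neither the H1N1 nor the H3N2 row. It is treated as a negative, and nothing in the table shows the reader that this has happened. The same holds for B specimens without a lineage.

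The printed share then mixes two quantities: how common the subtype or lineage is, and how many specimens the laboratory typed. If typing completeness differs between years, seasons or countries, part of any difference in the tables reflects laboratory effort and not circulating virus. This matters in a study meant to document B-lineage co-circulation across seasons.

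**Working it through.** **Inputs.** Protocol Table 2 (Panama, 2010-2014) gives influenza positives of 207, 47, 276, 190 and 140, of which B are 14, 0, 178, 0 and 55. The minimum and maximum, 47 and 276, reproduce the range stated in protocol section 5.2. For 2012, A = 276 - 178 = 98, and the B share is 178/276 = 64.5%. The typed fraction f is not in the documents and is varied here as an assumption.

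**Step 1: Victoria and Yamagata together, 2012.** Two denominators fit the titles: all positives, or all positives less the untyped B.

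| f (B typed) | All positives: f×178/276 | Untyped B dropped, A kept: f×178/(98 + f×178) |
|---|---|---|
| 25% | 44.5/276 = 16.1% | 44.5/142.5 = 31.2% |
| 50% | 89/276 = 32.2% | 89/187 = 47.6% |
| 75% | 133.5/276 = 48.4% | 133.5/231.5 = 57.7% |
| 100% | 178/276 = 64.5% | 178/276 = 64.5% |

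Both columns lie below 64.5% whenever typing is incomplete. The second is closer but still depends on f.

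**Step 2: one printed row.** Assume that 60% of B is Victoria and that typing does not depend on lineage. Counts are rounded to whole specimens, and the intervals are Clopper-Pearson 95%.

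| f | All positives | Untyped B dropped, A kept | Among lineage-typed B |
|---|---|---|---|
| 100% | 107/276 = 38.8% (33.0-44.8) | 38.8% | 107/178 = 60.1% (52.5-67.4) |
| 75% | 80/276 = 29.0% | 80/232 = 34.5% | 80/134 = 59.7% (50.9-68.1) |
| 50% | 53/276 = 19.2% (14.7-24.4) | 53/187 = 28.3% | 53/89 = 59.6% (48.6-69.8) |
| 25% | 26/276 = 9.4% | 26/142 = 18.3% | 26/44 = 59.1% (43.2-73.7) |

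With half of B typed, the exact interval on all positives excludes the 38.8% that full typing would give. Only the last column stays put as f changes; its interval widens instead.

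**Step 3: the A side.** With 98 A specimens and an assumed 60% H3N2, the all-positives share is 21.4%, 15.9%, 10.5% and 5.1% at f = 100%, 75%, 50% and 25%. With untyped A dropped and B kept it is 21.4%, 17.5%, 12.8% and 6.9%. Among subtyped A it is 60.2%, 59.5%, 59.2% and 58.3%.

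**Step 4: what is not an artefact.** Even with full typing, the two lineages together cannot exceed 64.5% in 2012 or 55/140 = 39.3% in 2014, because A specimens are in N. That follows from choosing all influenza as the base and is legitimate.

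**The case against.** The best defence is section 11.2.2. SAP section 6 says that the Annex 1 rules apply throughout without being repeated, and section 11.2.2 bases percentages on available information only. The footnote carries the same qualifier, and the introduction to Annex 3 says that mock titles and footnotes are illustrative and will be adapted. A programmer could therefore drop untyped specimens. This stands to the extent that a reader who infers that the SAP definitely keeps untyped specimens in N goes further than the text allows. It does not settle the matter. Section 11.2.2 also calls for counts of unknowns, which these templates have no place for, and dropping only the untyped specimens while the other type stays in N still understates the share (step 1).

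Three other inferences are tempting and not supported:

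- **That dropping untyped B reverses the bias.** The lineage share remains too low, only by less.
- **That the whole primary analysis is affected.** The by-age tables (12 and 13) exclude unknowns. Templates 7-10 belong to the month-and-year distribution, and Templates 20 and 22 to the seasonal analysis. Only Templates 19 and 21 plausibly serve the primary objective. Whether their totals disagree with Templates 12 and 13 depends on how untyped and other-type specimens are coded there.
- **That a real trend would be reversed.** If 50% of B were typed in 2012 and 90% in 2014, the combined lineage share would print as 32.2% and then 0.9×55/140 = 35.4%, while the B share fell from 64.5% to 39.3%. Those typing fractions are invented, no template prints the two lineages combined, and Template 17 reports the B share directly. The remark about non-routine typing concerns the other countries, not Panama.

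**Conclusion.** The point holds as an undefined denominator with a predictable consequence. The titles, the column header and the shared footnote make all influenza positives the natural reading of Templates 7-10 and 19-22. On that reading subtype and lineage shares are understated in proportion to the untyped fraction. On the alternative that still respects the titles they are understated less, but still move with typing effort whenever both types circulate. Either way the templates fit poorly with section 11.2.2 and with Templates 12, 13, 15, 16 and 23.

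The size cannot be determined from the documents. It is nil if every specimen is typed; the percentages above rest on assumed typing fractions, and those for single subtypes or lineages also on an assumed 60% share and on typing being unrelated to subtype or lineage. The lineage match table is outside this point, because it already uses specimens with available results.

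**What to change.** In Templates 7-10 and 19-22:

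1. State which result must be available for a specimen to enter N.
2. Add count rows 'A, not subtyped' and 'B, lineage not determined', and print the percentage typed for each period.
3. Report H1N1 and H3N2 shares among subtyped A, and Victoria and Yamagata shares among lineage-typed B. Use the planned Clopper-Pearson interval where the template has one, and print 'not estimable' when the denominator is 0, as it would be for lineage in Panama in 2011 and 2013. Show these beside the A and B shares of all influenza already in Templates 17-18.
4. If a subtype or lineage share of all influenza positives is kept, label it a lower bound for any period with incomplete typing.
5. State that the among-typed shares assume that, within type and period, typing does not depend on subtype or lineage.

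The cost is SAP wording and a little programming. Intervals will be wider where few specimens are typed: in the 2012 illustration, the among-typed interval goes from 52.5-67.4% at full typing to 43.2-73.7% at 25%.

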**Template 20 Proportion of Influenza A subtypes among all influenza cases by influenza season - <country> (Total cohort)**

<Southern/northern hemisphere influenza season>	Influenza A subtypes	n	N	%	95% CI	
					LL	UL
May– Oct 2010	H1N1					
	H3N2					
May– Oct 2011	H1N1					
	H3N2					
May– Oct 2012	H1N1					
	H3N2					
May– Oct 2013	H1N1					
	H3N2					
May– Oct 2014	H1N1					
	H3N2					
May– Oct 2015	H1N1					
	H3N2					
May– Oct 2016	H1N1					
	H3N2					
Total	H1N1					
	H3N2					

[figure not shown]
N = Number of Influenza positive specimens with available test results by year

n = Number of positive specimens in a given category

% = n/N \* 100

95%CI= exact confidence interval; LL=lower limit; UL=upper limit

**Figure 13 Distribution of Influenza A subtypes among all influenza cases by calendar year - <country> (Total cohort)**

**Figure 14 Distribution of Influenza A subtypes among all influenza cases by influenza season - <country> (Total cohort)**

Refer to [Figure 13](#)

**Template 21 Proportion of Influenza B lineage among all influenza cases by calendar year - <country> (Total cohort)**

Year	Influenza B lineage	n	N	%	95% CI	
					LL	UL
2010	Victoria					
	Yamagata					
2011	Victoria					
	Yamagata					
2012	Victoria					
	Yamagata					
2013	Victoria					
	Yamagata					
2014	Victoria					
	Yamagata					
2015	Victoria					
	Yamagata					
2016	Victoria					
	Yamagata					
Total	Victoria					
	Yamagata					

N = Number of Influenza positive specimens with available test results by year

n = Number of positive specimens in a given category

% =  $n/N * 100$

95%CI= exact confidence interval; LL=lower limit; UL=upper limit

**Template 22 Proportion of Influenza B lineage among all influenza cases by influenza season - <country> (Total cohort)**

<Southern/northern hemisphere influenza season>	Influenza B lineage	n	N	%	95% CI	
					LL	UL
May– Oct 2010	Victoria					
	Yamagata					
May– Oct 2011	Victoria					
	Yamagata					
May– Oct 2012	Victoria					
	Yamagata					
May– Oct 2013	Victoria					
	Yamagata					
May– Oct 2014	Victoria					
	Yamagata					
May– Oct 2015	Victoria					
	Yamagata					
May– Oct 2016	Victoria					
	Yamagata					
Total	Victoria					
	Yamagata					

[figure not shown]
N = Number of Influenza positive specimens with available test results by year

n = Number of positive specimens in a given category

% =  $n/N * 100$

95%CI= exact confidence interval; LL=lower limit; UL=upper limit

**Figure 15 Distribution of Influenza B lineage among all influenza cases by calendar year - <country> (Total cohort)**

**Figure 16 Distribution of Influenza B lineage among all influenza cases by influenza season - <country> (Total cohort)**

Refer to Figure 15

**Template 23 Comparison of influenza B virus vaccine lineage and circulating lineage in the population by influenza season - <country> (Total cohort)**

<Southern/northern hemisphere influenza season>	Circulating Influenza B lineages			Vaccine Recommendation*	% Match	% Mismatch
	B lineage	n	%			
2010	Victoria			Victoria		
	Yamagata			Victoria		
2011	Victoria			Victoria		
	Yamagata			Victoria		
2012	Victoria			Victoria		
	Yamagata			Victoria		
2013				Yamagata		
2014				Yamagata		
2015						
2016						

[figure not shown]
\*<http://www.who.int/influenza/vaccines/virus/recommendations/en/>

n = Number of influenza positive specimens in a given category

% = n / Number of specimens with available results x 100

% Mismatch = 100% - % Circulating B lineage match with vaccine

**Figure 17 Circulation of influenza B lineage by season and recommended vaccine composition - <country> (Total cohort)**

**Template 24 Summary of signs and symptoms by influenza types and influenza season - <country> (Total cohort)**

<Southern/northern hemisphere influenza season>	Signs and symptoms	Categories	Influenza A positive N=XX		Influenza B positive N=XX		Influenza virus positive N = XX	
			n	%	n	%	n	%
May– Oct 2010	Sudden onset of symptoms	Yes						
		No						
		Unknown	-		-			
	Fever	Yes						
		No						
		Unknown	-		-			
	Malice	Yes						
		No						
		Unknown	-		-			
	Cough	Yes						
		No						
		Unknown	-		-			
	Rhinorrhea	Yes						
		No						
		Unknown	-		-			
	Headache	Yes						
		No						
		Unknown	-		-			
	Polypnea	Yes						
		No						
		Unknown	-		-			

## CONFIDENTIAL

205049 (EPI-FLU-052 BOD PA DB)

Statistical Analysis Plan Final

			Influenza A positive N=XX	Influenza B positive N=XX	Influenza virus positive N = XX
	Dyspnea	Yes			
		No			
		Unknown	-	-	-
	Vomiting	Yes			
		No			
		Unknown	-	-	-
	Myalgia	Yes			
		No			
		Unknown	-	-	-
	Arthralgia	Yes			
		No			
		Unknown	-	-	-
	Irritability	Yes			
		No			
		Unknown	-	-	-
	Odynophagia	Yes			
		No			
		Unknown	-	-	-
	Abdominal pain	Yes			
		No			
		Unknown	-	-	-
	Diarrhea	Yes			
		No			
		Unknown	-	-	-
	Conjunctivitis	Yes			
		No			
		Unknown	-	-	-
	Chest pain	Yes			
		No			
		Unknown	-	-	-
	Cyanosis	Yes			
		No			
		Unknown	-	-	-
	Chills	Yes			
		No			
		Unknown	-	-	-
May– Oct 2011					
May– Oct 2012					
...					
...					
Total					

N = number of influenza positive specimens by groups

n = number of positive specimens in a given category

% = n / Number of subjects with available results x 100

**Template 25 Summary of signs and symptoms by influenza A subtypes and B lineage and influenza season - <country> (Total cohort)**

		Signs and symptoms	Influenza A subtypes		Influenza B lineage			
			H1N1 N=XX		H3N2 N=XX		Victoria N=XX	
			n	%	n	%	n	%
<Southern/northern hemisphere influenza season>	May– Oct 2010	Sudden onset of symptoms	Yes					
			No					
			Unknown				-	-
		Fever	Yes					
			No					
			Unknown				-	-
		Malice	Yes					
			No					
			Unknown				-	-
		Cough	Yes					
			No					
			Unknown				-	-
		Rhinorrhea	Yes					
			No					
			Unknown					
		Headache	Yes					
			No					
			Unknown				-	-
		Polypnea	Yes					
			No					
			Unknown				-	-
		Dyspnea	Yes					
			No					
			Unknown				-	-
		Vomiting	Yes					
			No					
			Unknown				-	-
		Myalgia	Yes					
			No					
			Unknown				-	-
		Arthralgia	Yes					
			No					
			Unknown				-	-
		Irritability	Yes					
			No					
			Unknown				-	-

		Influenza A subtypes			Influenza B lineage	
		H1N1 N=XX	H3N2 N=XX	Victoria N=XX	Yamagata N=XX	
	Odynophagia	Yes				
		No				
		Unknown		-	-	
	Abdominal pain	Yes				
		No				
		Unknown		-	-	
	Diarrhea	Yes				
		No				
		Unknown		-	-	
	Conjunctivitis	Yes				
		No				
		Unknown		-	-	
	Chest pain	Yes				
		No				
		Unknown		-	-	
	Cyanosis	Yes				
		No				
		Unknown		-	-	
	Chills	Yes				
		No				
		Unknown		-	-	
	May- Oct 2011					
	May- Oct 2012					
	...					
	Total					

N = number of influenza positive specimens by groups

n = number of positive specimens in a given category

% = n / Number of specimens with available results x 100

**Template 26 Summary of co-morbidity conditions by influenza types and influenza season- <country> (Total cohort)**

<Southern/northern hemisphere influenza season>	Co-morbidity condition	Categories	Influenza A positive N=XX		Influenza B positive N=XX		Influenza virus positive N = XX	
			n	%	n	%	n	%
May- Oct 2010	Diabetes	Yes						
		No						
		Unknown	-		-		-	
	Chronic obstructive pulmonary disease (COPD)	Yes						
		No						
		Unknown	-		-		-	
	Asthma	Yes						
		No						
		Unknown	-		-		-	

## CONFIDENTIAL

205049 (EPI-FLU-052 BOD PA DB)

Statistical Analysis Plan Final

			Influenza A positive N=XX	Influenza B positive N=XX	Influenza virus positive N = XX
<Southern/northern hemisphere influenza season>	Co-morbidity condition	Categories	n	%	n
	Immunosuppression	Yes			
		No			
		Unknown	-	-	-
	Hypertension	Yes			
		No			
		Unknown	-	-	-
	HIV/AIDS	Yes			
		No			
		Unknown	-	-	-
	Cardiovascular disease	Yes			
		No			
		Unknown	-	-	-
	Obesity	Yes			
		No			
		Unknown	-	-	-
	Smoking	Yes			
		No			
		Unknown	-	-	-
	Chronic renal failure	Yes			
		No			
		Unknown	-	-	-
	Pregnancy	Yes			
		No			
		Unknown	-	-	-
	Months of pregnancy	n	-	-	-
		Mean	-	-	-
		SD	-	-	-
		Median	-	-	-
		Minimum	-	-	-
		Maximum	-	-	-
		N.A./Unknown	-	-	-
May– Oct 2011					
...					
....					
Total					

N = number of influenza positive specimens by groups

n = number of influenza positive specimens in a given category

% = n / Number of specimens with available results x 100

**Template 27 Summary of co-morbidity conditions by influenza A subtypes and B lineage and influenza season- <country> (Total cohort)**

		Co-morbidity condition	Categories	Influenza A subtypes		Influenza B lineage	
				H1N1 N=XX	H3N2 N=XX	Victoria N=XX	Yamagata N=XX
<Southern/northern hemisphere influenza season>							
May– Oct 2010		Diabetes	Yes				
			No				
			Unknown	-	-	-	-
		Chronic obstructive pulmonary disease (COPD)	Yes				
			No				
			Unknown	-	-	-	-
		Asthma	Yes				
			No				
			Unknown	-	-	-	-
		Immunosuppression	Yes				
			No				
			Unknown	-	-	-	-
		Hypertension	Yes				
			No				
			Unknown	-	-	-	-
		HIV/AIDS	Yes				
			No				
			Unknown	-	-	-	-
		Cardiovascular disease	Yes				
			No				
			Unknown	-	-	-	-
		Obesity	Yes				
			No				
			Unknown	-	-	-	-
		Smoking	Yes				
			No				
			Unknown	-	-	-	-
		Chronic renal failure	Yes				
			No				
			Unknown	-	-	-	-
		Pregnancy	Yes				
			No				
			Unknown	-	-	-	-
		Months of pregnancy	n	-	-	-	-
			Mean	-	-	-	-
			SD	-	-	-	-
			Median	-	-	-	-
			Minimum	-	-	-	-
			Maximum	-	-	-	-
			N.A./Unknown	-	-	-	-
May– Oct 2011							
...							
Total							

N = number of influenza positive specimens by groups

n = number of positive specimens in a given category

% = n / Number of specimens with available results x 100

**Template 28 Summary of treatments by influenza types and influenza season-  
<country> (Total cohort)**

			Influenza A positive N=XX		Influenza B positive N=XX		Influenza virus positive N = XX	
<Southern/northern hemisphere influenza season>	Treatment	Categories	n	%	n	%	n	%
May– Oct 2010	Treatment received from the beginning of symptoms	Yes						
		No						
		Unknown		-		-		-
	Antivirals treatment	Yes						
		No						
		Unknown/NA		-		-		-
	Microbial Treatment	Yes						
		No						
		Unknown/NA		-		-		-
May– Oct 2011								
...								
Total								

N = number of influenza positive specimens by groups

n = number of positive specimens in a given category

% = n / Number of specimens with available results x 100

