1.3. Rationale for the study

Evidence is needed to assess prevalence and incidence of seasonal influenza A & B, assess the potential mismatch and identify clinical features of seasonal Influenza A and B by country and in this region. Thus, this study aims to raise awareness to the public health stakeholders the need for quadrivalent influenza vaccine (QIV) and support its recommendation by:

- Generating burden of disease data that highlights the contribution of influenza to hospitalization, mortality, cardiovascular disease and other complications.
- Providing evidence and documenting the mismatch between circulating B strains and those included in the recommended trivalent seasonal vaccines and B-lineage co-circulation of influenza across different seasons.
- Understanding the burden of disease caused by influenza B strains and the added value of a QIV.

The data from this study,

- may support the implementation and expansion of existing universal mass vaccination (UMV) strategies for influenza.
 - the current recommendation is to vaccinate the elderly, health care workers, children (in some countries vaccination is limited to children with chronic diseases), adults with chronic diseases. Some countries in the study region also recommend influenza vaccination in pregnant women [[TAG recommendations for influenza vaccination, 2014](#)]
- can provide robust and reliable data to develop future HE model adaptations in the selected study regions.
- may provide evidence of the added value of deploying QIVs and thus further support the need and recommendation for QIVs for different age groups.

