#### **5.1.2. Total cohort**

The Total cohort will comprise of all eligible subjects included in the study.

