## 9. CHANGES FROM PLANNED ANALYSES

- There will be an interim analysis planned on available data (lab database for Panama) in order to submit the abstract\poster for SLIPE congress
- We will also be reporting the number of specimen samples received per year within the ICGES influenza surveillance system for influenza testing at aggregated level (considered as screened cohort) and determine the proportion that tested positive for Influenza to describe the reporting capabilities of the surveillance system at capturing influenza A and B cases.
- We will also be including seasonal 2016 data as it is presently available. Based on the dates of data transfer, the end time period may be expanded if data is available during data transfer
- All the statistical analysis will be performed on specimens instead of subjects because a subject can provide more than one influenza positive specimens.
- The age group used for the analysis are 0-4, 5-17, 18-49, 50-64 and >=65 years instead of <1, 1-4, 5-9, 10-14, 15-19, 20-24, 25-44, 45-49, 50-59, 60-64 and ≥ 65 years.

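### The Pregnancy percentage in SAP Templates 26–27 is not limited to those who could be pregnant, so it can be diluted and can shift with source coding and with age and sex mix

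*SAP*

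**What the plan says.** SAP Annex 3, Template 26 (by influenza type and season) and Template 27 (by A subtype, B lineage and season) list Pregnancy among the co-morbidity conditions, with the lines Yes, No and Unknown. The footnotes separate two quantities. The column total is "N = number of influenza positive specimens by groups". The percentage is "n / Number of specimens with available results x 100".

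Both templates use the Total cohort, which SAP 5.1.2 defines without any sex or age limit: "The Total cohort will comprise of all eligible subjects included in the study". SAP section 9 confirms that children and older adults are in it: "The age group used for the analysis are 0-4, 5-17, 18-49, 50-64 and >=65 years".

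The next row, "Months of pregnancy", has a combined line for not applicable and unknown. So do the antiviral and microbial treatment rows of Templates 28 and 29. The Pregnancy row has none.

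SAP 11.2.2 gives the general rule: "The percentages will be computed by using only available information". It continues: "Only frequencies will be provided for unknown or missing or not applicable categories". Nothing in the SAP says how males, children or older women are to be classed on the Pregnancy item.

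**The concern.** Pregnancy differs from the other rows in the table. *No diabetes* is informative for anyone. *Not pregnant* is informative only for someone who could be pregnant. Under the footnote, a man or a five-year-old recorded as *No* has an available result and is counted in the denominator. The same person left blank or coded not applicable is not counted. The percentage then depends on how forms were completed for people to whom the question does not apply.

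The item has some relevance to the study's purpose. Protocol 1.3 names the group when it sets out vaccination policy: "Some countries in the study region also recommend influenza vaccination in pregnant women". A reader will take the figure as the frequency of pregnancy among relevant cases and will read it across the virus columns. If the denominator carries the age and sex mix, columns can differ with no difference among women who could be pregnant.

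**Working it through.** The plan prints no pregnancy percentage, so there is no figure to reproduce. The check asks what the stated rule would print.

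**Inputs**
- Denominator: specimens with an available result (footnotes to Templates 26 and 27).
- s, the share of females of child-bearing age among positives: not in the documents; assumed 10% to 35%.
- p, the pregnancy prevalence among them: not in the documents; assumed 10%, with 5% to 20% as a range.
- f, the fraction of everyone else coded *No* rather than blank, unknown or not applicable: not in the documents; varied from 0 to 1.
- Every eligible female is taken to have a known status, and no one else is recorded as pregnant.

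**Formula**

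Printed % = 100 × p·s / (s + f·(1 − s))

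With f = 1 this is 100 × p·s. With f = 0 it is 100 × p.

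**Effect of coding, p = 10%**

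| s | f = 1 (all others *No*) | f = 0.5 | f = 0 (none *No*) |
|---|---|---|---|
| 10% | 0.10 × 0.10 = 1.0% | – | 10.0% |
| 15% | 0.10 × 0.15 = 1.5% | 0.015/0.575 = 2.6% | 10.0% |
| 25% | 0.10 × 0.25 = 2.5% | 0.025/0.625 = 4.0% | 10.0% |
| 35% | 0.10 × 0.35 = 3.5% | – | 10.0% |

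At f = 1 the dilution factor is 1/s: 10-fold at s = 10%, and 2.9-fold at s = 35%. Over p = 5% to 20%, the printed figure at f = 1 runs from 0.05 × 0.10 = 0.5% to 0.20 × 0.35 = 7.0%.

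**Effect of mix, p = 10% in both columns, f = 1**
- s = 25% for A and 25% for B: 2.5% and 2.5%, no difference.
- s = 25% for A and 15% for B: 2.5% and 1.5%, ratio 1.67.
- s = 30% for A and 10% for B: 3.0% and 1.0%, ratio 3.0.

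**With a restricted denominator**, the printed figure is p·s/s = p, here 10.0%, for any s and f.

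**Denominators after restriction.** Protocol Table 2 gives Panama influenza B positives of 14, 0, 178, 0 and 55 for 2010 to 2014. At s = 10% these leave about 1.4, 0, 17.8, 0 and 5.5 eligible specimens. At s = 35% they leave 4.9, 0, 62.3, 0 and 19.3. Over the five years, 247 B positives leave about 25 to 86. The other 860 − 247 = 613 positives leave about 61 to 215. All of these are before splitting by subtype or lineage, before limiting to the May to October season, and before removing unknown status.

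**The case against.** The strongest reply is that the plan may produce no dilution at all. The denominator is specimens with an available result, not the column total, and SAP 11.2.2 already keeps not-applicable records out of percentages. SAP section 6 applies the Annex 1 rules throughout. If the source leaves the item blank or not applicable for males and children, the printed figure is already the right one. This stands, and it is why the size cannot be stated. It does not close the gap, because 11.2.2 removes only records already coded that way, and no rule recodes a *No* in someone who could not be pregnant.

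A reader might infer that pregnancy is planned as a percentage of all influenza-positive specimens, or that the A and B columns will differ for this reason. The documents support neither. The first contradicts the footnote. The second needs both *No* coding and a different age and sex mix, and the documents give no data on either. Nor are there country columns, since the templates are produced separately for each country.

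Other fair points:
- Annex 3 calls the mock tables illustrative and allows minor changes without an amendment, so the absent line is weak evidence about the final layout. The missing eligibility rule is a gap wherever the table is finalised.
- The share of all cases who are pregnant is a legitimate description, and Templates 3 and 4 show the age and gender mix. But the footnote does not deliver that figure either, unless everyone else is coded *No*.
- The analyses are descriptive (SAP section 7), and co-morbidity is not a listed endpoint. This limits the impact, but a descriptive percentage still needs a defined denominator.

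**Conclusion.** The point holds as a denominator that is not limited to those eligible for the item. Following the stated rule, anyone recorded as *No* counts, whether or not they could be pregnant. The percentage can therefore be diluted, and can move with source coding and column mix.

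That the rule permits this is clear from the text. Whether it will happen, and by how much, is not known. Under the assumed 10% prevalence and 10% to 35% share, the same data print anywhere from 1.0% to 3.5% with full *No* coding, against 10% with none. Those inputs are illustrations, not estimates for this database. The consequence is confined to one descriptive row in two templates and touches no primary or secondary endpoint.

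**What to change.** In Templates 26 and 27:
- Compute the Pregnancy Yes and No percentages only in female specimens within a pre-stated child-bearing age range (for example 15–49 years at onset) with known pregnancy status.
- Print the number eligible and the number with unknown status.
- Put all other specimens in a not-applicable line as counts only, as SAP 11.2.2 already provides.
- List as counts the specimens with missing age or sex, and any pregnancy recorded outside the range.

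This gives the same figure however the source coded everyone else. It needs a footnote and a programming filter on age and gender, which Protocol 6.5.3 already extracts. The 15–49 range does not match the SAP age groups (5–17, 18–49), so the filter must use individual age. SAP 11.2.2 derives age only where the dates exist, hence the count of unclassifiable specimens.

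The main cost is small denominators in some season and lineage cells. Counts should be shown beside the percentages, and the Total row used for reading the result.
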